6.1.3. Reporting Serious Adverse Events

All SAEs that occur from time of informed consent until completion of the final visit, whether considered to be associated with the study medication or not, must be reported within 24 hours by telephone, e-mail, or fax to the Sponsor's Medical Monitor and/or Sponsor's designee using the appropriate contact details provided. The minimum information required for an initial report is:

- Sender of report (name, address of Investigator),
- Subject identification (subject number, NOT subject name),
- Protocol number,
- Description of SAE and date of onset,
- Relationship assessment,
- Date of visit and study visit number,
- Current status of subject.

However, whenever possible, all points on the SAE form should be completed and the form faxed or scanned and emailed to the Sponsor or designee. The site should also notify the Sponsor or designee by email or voicemail if the information was sent via facsimile. In addition, the event must be documented in the CRF.

It is recognized that it may be difficult to differentiate the relationship of an adverse event to CST-2032 or to CST-107 (nadolol). There is a long history of the clinical safety of nadolol and the dose of nadolol being administered in this study is less than 10% of the labeled starting dose for treatment of angina pectoris or hypertension (3 mg versus 40 mg). Therefore, unless the PI is confident in attribution of causality to CST-107 (e.g., for an AE that occurs prior to administration of CST-2032), all assessments of related AEs will be attributed to CST-2032 for expedited reporting purposes.

After receipt of the initial report, the Sponsor's Medical Monitor or designee will review the information and, if necessary, contact the Investigator to obtain further information for assessment of the event. The Sponsor or designee will be responsible for all information processing and reporting according to local legal requirements.

The Sponsor or designee will determine the SAEs requiring expedited reporting to regulatory agencies. The clinical trial site personnel are responsible for reporting these events to their Ethics Committee in accordance with applicable laws and regulations.

6.1.4. Follow-up of Adverse Events

All AEs and SAEs experienced by a subject, irrespective of the suspected causality, will be monitored until the event has resolved, until any abnormal laboratory values have returned to baseline or stabilized at a level acceptable to the Investigator and Medical Monitor. Any SAE that occurs after final visit but is felt to be related to the study medication by the Investigator

must be reported to Sponsor or designee and any necessary regulatory agencies and must be followed by the Investigator until resolution or stabilization.

6.2. Clinical Safety Laboratory Abnormalities

Blood and urine samples for routine safety laboratory parameters will be collected at timepoints specified in the Schedule of Events. The Investigator will document review of all labs and will determine and document clinical significance. All abnormal laboratory values that are clinically significant, treatment-emergent, and meet one of the following conditions (as determined by the Investigator) should be recorded as a single AE:

- Accompanied by clinical symptoms, or
- Requires a change in concomitant therapy

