3.2. Criteria for Termination of Study Medication

Dosing of the study medication will be terminated for any subject for whom either of the following circumstances apply:

- Subject experiences a serious adverse event (SAE) that is deemed by the investigator to be related to study medication
- Medical or ethical reasons affecting continued participation in the study.
- Dosing of the study medication may be stopped if treatment-related AEs, changes in vital signs, ECG or clinical laboratory results are observed and these changes pose a significant health risk, in the opinion of the CuraSen Medical Monitor or Principal Investigator (PI).

A subject may be terminated at any point in time at the discretion of CuraSen Medical Monitor or PI.

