3.3. Criteria for Suspension/Termination of Trial

Administration of CST-2032 and CST-107 will be stopped if either of the following occurs:

- Two serious adverse events (SAEs) within the same system organ class (SOC) considered to be related to study drug; or
- Three severe or clinically significant adverse events (AEs) considered to be related to study drug.

The Sponsor reserves the right to terminate this clinical trial at any time. If the clinical trial is terminated prior to scheduled completion, the Investigator will be notified and given any necessary instructions concerning final examinations that are required. If the Investigator, the Sponsor, or the Sponsor's Medical Monitor becomes aware of conditions or events that suggest a possible hazard to subjects if the clinical trial continues, the clinical trial may be terminated after appropriate consultation with the relevant parties.

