6.1. Adverse Events

6.1.1. Definitions

Adverse Event

An AE is any untoward medical occurrence associated with the use of a study drug in humans and which does not necessarily have a causal relationship with this treatment. AEs

may be reported by the subject, discovered through Investigator questioning, or detected through physical examination, laboratory test, or other means.

AEs include:

- Any new undesirable medical experience or an unfavorable and unintended change of an existing condition that occurs during or after treatment, whether or not considered related to study medication.
- Abnormal laboratory findings considered by the Investigator to be clinically significant, i.e., those that are unusual for the population being studied or individual subject.
- Complications and termination of pregnancy; uncomplicated pregnancies are not considered AEs but must still be reported.

Additionally, events (including intercurrent illnesses) occurring from the time of randomization will be documented on the AE CRF. Concurrent illnesses, which existed prior to first dose in the clinical trial, will not be considered AEs unless they worsen during the treatment period.

Serious Adverse Event

An SAE is defined as any untoward medical occurrence that at any dose:

- Results in death.
- Is life-threatening (this means that the subject is at risk of death at the time of the event; it does not mean that the event hypothetically might have caused death if it were more severe).
- Requires or prolongs subject hospitalization.
- Results in persistent or significant disability or incapacity.
- Is a congenital anomaly or birth defect.
- Is an important medical event that does not otherwise meet the criteria for seriousness.

Medical and scientific judgment should be exercised in deciding if an event is serious if it does not meet the above definitions, such as an important medical event(s) that may not be immediately life-threatening or result in death or hospitalization but that may jeopardize the subject or may require intervention to prevent one of the above outcomes. Specific examples of such events are intensive treatment in an emergency room or at home for allergic bronchospasm, blood dyscrasias, or convulsions that do not result in hospitalization.

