6.1.2.2. Relationship to Study Medication

The Investigator or designee, using clinical judgment, will assess the causality/relationship between each AE and the most recently administered study medication (i.e., whether there is a reasonable possibility that the drug caused the event) and record that assessment in the CRF.

Unrelated: The AE is clearly not related to the study medication. The AE is clearly explained by another cause, or exposure to the study medication has not occurred.

Related: The AE may be related to the study medication. The AE and administration of the study medication are considered reasonably related in time, but the AE is more likely explained by the study medication than another cause.

AE reporting will extend from randomization until completion of the End-of-Study Visit. AEs occurring after the end of the clinical trial must be reported if the Investigator considers there is a causal relationship with the study medication.

All AEs, regardless of the relationship to study medication, will be recorded in the CRF.

All reports should contain a brief description of the event, date of onset, date of resolution, severity, treatment required, relationship to study medication, outcome, and whether the event is classified as serious. Whenever possible, the Investigator should group signs or symptoms that constitute a single diagnosis into a single event term. For example, “cough, rhinitis, and sneezing” might be grouped together as “upper respiratory tract infection.”

A treatment-emergent clinically significant abnormal laboratory value should be recorded as an AE.

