11 SAFETY

11.1 Adverse Events

Adverse events (AEs) will be recorded from the time of randomization through end of study. AEs will also be assessed for severity, relationship to study drug, and seriousness. AEs will be considered treatment-emergent if their onset occurs following the date and time of first dose of CST-2032 or matching placebo up to the study completion date. Each TEAE will also be categorized according to the treatment period in which it occurs, in order to attribute and summarize an AE based on treatment received at time of event (i.e., during placebo or active treatment). Events that occur during the washout period between Treatment Period 1 and 2 will be attributed to the treatment received in Period 1, and events occurring after Treatment Period 2 up to the End of Study visit will be attributed to the treatment received in Period 2.

Any missing severity assessments will be assumed to be severe, missing relationship assessments will be assumed to be related, and missing seriousness assessments will be assumed as serious.

An overview of AEs will be produced, including counts and percentages of subjects with any incidences of: treatment-emergent AEs (TEAEs), serious AEs (SAEs), related AEs, unrelated AEs, AEs by maximum severity, AEs leading to treatment withdrawal and AEs leading to death.

Adverse events will be coded based on the Medical Dictionary for Regulatory Affairs (MedDRA 24.1) for reporting by system organ class (SOC) and preferred term (PT) in descending order of overall incidence.

Summaries of adverse events by SOC and PT will include the following types:

- TEAEs;
- SAEs; and
- Related AEs.

A summary of TEAEs by SOC, PT, and maximum severity will also be prepared.

A comprehensive listing of all AEs will be provided in a by-subject data listing. In addition, the following listings will be provided:

- SAEs;
- Related AEs; and
- AEs leading to study drug termination

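### Protocol 6.2 is narrower than 6.1.1 and 6.1.2.2 on when a clinically significant laboratory value is an adverse event, so sites that follow 6.2 would under-record laboratory AEs

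*Protocol*

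**What the plan says.** Three sections of the protocol say when a laboratory value becomes an AE.

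- Section 6.1.1 lists among AEs "Abnormal laboratory findings considered by the Investigator to be clinically significant". It explains significance as a result out of the ordinary for the study population or for that person. It sets no further condition.
- Section 6.1.2.2 says: "A treatment-emergent clinically significant abnormal laboratory value should be recorded as an AE". Again there is no further condition.
- Section 6.2 addresses "All abnormal laboratory values that are clinically significant, treatment-emergent, and meet one of the following conditions" and asks that these be recorded as one AE. The conditions are that the value comes with clinical symptoms, or "Requires a change in concomitant therapy".

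Other sections use the AE label.

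- Section 2.2 makes AE rates part of the primary endpoint, next to laboratory safety observations.
- Section 3.2 allows dosing to be halted for laboratory changes as well as for AEs: "Dosing of the study medication may be stopped if treatment-related AEs, changes in vital signs, ECG or clinical laboratory results are observed".
- Section 3.3 makes it mandatory to stop dosing after "Three severe or clinically significant adverse events (AEs) considered to be related to study drug".
- Section 6.1.4 requires AEs to be followed to resolution, or "until any abnormal laboratory values have returned to baseline or stabilized at a level acceptable to the Investigator and Medical Monitor".
- SAP 11.1 tabulates, among other counts, "AEs leading to treatment withdrawal and AEs leading to death". It takes AEs as recorded and has no rule of its own for laboratory values.

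**The concern.** A value can be treatment-emergent and clinically significant yet cause no symptoms and prompt no change in other medicines. Sections 6.1.1 and 6.1.2.2 make it an AE. Section 6.2, read as written, does not call for it to be recorded. Up to 20 sites could settle this in different ways, and the SAP would not correct the difference afterwards.

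Three things depend on the label: the AE rates in the primary endpoint, the tabulation of AEs that lead to treatment withdrawal, and the follow-up duty in 6.1.4. The mandatory stop in 3.3 may depend on it as well.

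The question is relevant to this drug. Protocol 1.1.1 names hypokalemia among the most common AEs of CST-2032 given alone, and a potassium change is the kind of finding that can be seen on a chemistry result before anyone feels it.

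**Working it through.** **Step 1. Compare the rules.** Take a laboratory value that is treatment-emergent and clinically significant, and ask what each section requires.

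| Case | 6.1.1 and 6.1.2.2 | 6.2 |
|---|---|---|
| With symptoms | AE | AE |
| No symptoms, another medicine started or changed | AE | AE |
| No symptoms, no other medicine changed | AE | Not called for |
| As the row above, but study drug stopped under 3.2 | AE | Not called for |

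The sections differ in the last two rows. The fourth row follows because study drug is not concomitant therapy, so stopping it does not meet the second condition in 6.2. Such a stop could then be missing from the SAP 11.1 count of AEs leading to withdrawal.

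**Step 2. Test whether 6.2 could be a grouping rule only.** It asks for a *single* AE, which might mean one entry for a value and its symptoms. That suits the first condition. It suits the second poorly: a value that only requires a change of medicine has no symptom to be grouped with. If every clinically significant value were recorded anyway, the conditions would do little. The filter is therefore the more natural reading, though not the only possible one.

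**Step 3. Trace the link to 3.3.** The stop counts related AEs that are severe or clinically significant. Section 6.1.2.1 grades AEs as mild, moderate or severe, and nothing defines a clinically significant AE. In 6.1.1 the words describe a laboratory finding; in 3.3 they describe an event. Whether the first implies the second is not stated.

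**Step 4. Size, conditionally.** The documents give no rate, so there is no plan figure to reproduce. The following is an illustration.

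- *n* = 60, the planned sample (Protocol 8.1), all assumed to receive active drug.
- *p* = assumed chance per subject of a related, clinically significant, treatment-emergent laboratory abnormality, at most one each, independent.
- *f* = assumed share of these that meet a condition in 6.2.
- Every recorded one is assumed to count in 3.3, and no other AE is counted.

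With *q* = *p* under 6.1.2.2 and *q* = *f* × *p* under 6.2:

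P(3 or more) = 1 − [(1−q)^60 + 60q(1−q)^59 + 1770q²(1−q)^58]

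For q = 0.02: 1 − [0.2976 + 0.3644 + 0.2194] = 0.119.

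| p | Expected number, 60p | 6.1.2.2 | 6.2, f = 50% | 6.2, f = 25% | 6.2, f = 0 |
|---|---|---|---|---|---|
| 1% | 0.6 | 2.2% | 0.35% | 0.05% | 0 |
| 2% | 1.2 | 11.9% | 2.2% | 0.35% | 0 |
| 5% | 3.0 | 58.3% | 19.0% | 4.0% | 0 |
| 10% | 6.0 | 94.7% | 58.3% | 19.0% | 0 |

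Under 6.1.2.2 the chance passes 10% at *p* of about 1.9% and 50% at about 4.4%. The zero column is zero by construction.

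**Step 5. Which rows are plausible.** The documents support none of these rates, and what they say about potassium points to the low end. Protocol 1.1.1 reports no clinically significant fall in potassium at 3 mg of each drug, and observed potassium of 3.8 to 4.3 mmol/L with 1, 3 or 10 mg CST-2032 plus 3 mg nadolol. Section 4.3 excludes a history of hypokalemia and gives potassium below normal as an example of an excluding finding. This evidence covers potassium only, and 1.1.1 describes repeat dosing at 3 mg for 7 days, against 14 here.

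**The case against.** The strongest reply is that 6.2 never says *only*. It does not declare other values not to be AEs, and 6.1.2.2 is explicit. A site that records every treatment-emergent, clinically significant value complies with all three sections; a site that omits one breaches 6.1.2.2. This is right about strict compliance. It does not help a site that goes to 6.2, the section headed for laboratory abnormalities, and applies its conditions.

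A reader might infer that each related laboratory AE must count towards the three-event stop, because it is clinically significant by definition. The documents do not support that. The test in 6.1.1 is whether a result is unusual, while 3.3 sets the phrase beside *severe* and may call for a separate judgement about the event. On that view asymptomatic values need not count under any of the rules.

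A reader might also take the larger probabilities above as a forecast that the trial would stop. They are not one: 5% and 10% are assumptions without support, and each event must also be judged more likely due to study drug than to another cause.

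Nor would the laboratory signal be lost. Laboratory observations are in the primary endpoint in their own right (2.2), safety data including laboratory results are monitored blinded throughout (Protocol 6), and SAP 11.2 provides listings and shift tables. A DSMB is planned (3.4), and the PI, Medical Monitor or Sponsor can stop dosing or the trial by judgement (3.2, 3.3). Each subject is due to receive both treatments, so differences in practice between sites should not by themselves bias the comparison. All of this stands and limits the consequence. It does not settle which values are AEs.

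**Conclusion.** The inconsistency is real and is in current protocol text. On its natural reading 6.2 asks for fewer laboratory AEs than 6.1.1 and 6.1.2.2 require, and it can omit a laboratory change that leads to study drug being stopped. AE rates, AEs leading to withdrawal and AE follow-up are affected directly. The stop in 3.3 is affected only if a clinically significant laboratory value is also a clinically significant AE there, which the protocol leaves open.

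The size is unknown. If such values do count in 3.3, and at most 1% of subjects have one, the chance of reaching three from them alone is no more than 2.2% under the wider rule, so the choice of rule matters little. It would matter more at higher rates, which the documents do not support. The conclusion rests on reading 6.2 as a filter; a grouping-only reading remains possible but fits the second condition poorly. This is a gap in wording that deserves a clarifying amendment, not a flaw that hides laboratory toxicity.

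**What to change.** Reword 6.2, and refer to it from 6.1.1 and 6.1.2.2, along these lines: *Every treatment-emergent laboratory abnormality judged clinically significant by the Investigator is recorded as an AE, including one leading to a change in study drug dosing; an abnormality and its associated symptoms are recorded as a single AE.* This keeps the grouping instruction and removes the filter.

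In 3.3, add one sentence saying whether asymptomatic laboratory AEs count towards the three events.

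A listing in the SAP of post-dose values marked clinically significant but not recorded as AEs is optional. Section 6.2 already has the Investigator document significance for all laboratory results, so it needs no new assessment at site, provided that the mark is held in the database.

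The cost is a small protocol amendment and somewhat more AEs recorded. If asymptomatic laboratory AEs are then counted in 3.3, the stop becomes easier to reach, which is why that section should state the choice.

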6.3. ECG Abnormalities

All ECGs will be evaluated by a central ECG reader and the Investigator in consultation with the Sponsor's Medical Monitor to determine if the abnormality is significant and whether it is safe for the subject to continue in the study.

6.4. Pregnancy

Female subjects who become pregnant during the study period must be discontinued from the study. Pregnancy in a study subject should be reported by the Investigator within 1 business day to the Sponsor's Medical Monitor. Pregnancy in itself is not regarded as an AE unless there is a suspicion that an investigational product may have interfered with the effectiveness of a contraceptive medication.

Any female subject or partner of a male study subject who becomes pregnant during the trial will be asked to agree to regular reporting of the progress and outcome of her pregnancy to the Investigator (or designee) and Sponsor. Monitoring of the pregnant subject or partner should continue until the outcome (spontaneous miscarriage, elective termination, normal birth, or congenital abnormality) of the pregnancy is known and documented even if the subject was discontinued from the study.

All reports of congenital abnormalities/birth defects are SAEs. Spontaneous miscarriages should also be reported and handled as SAEs. Elective abortions without complications should not be handled as AEs.

7. STUDY MEDICATION

7.1. Study Medication

CST-2032 is provided as white tablets containing 3 mg CST-2032 that are identical in appearance to the matching placebo. CST-2032 and matching placebo will be supplied in blister cards containing 10 repeat doses for a 1-week supply.

CST-107 is provided as yellow tablets containing 3 mg nadolol that are identical in appearance to the matching placebo. CST-107 and matching placebo will be supplied in blister cards or bottles containing 10 repeat doses for a 1-week supply.

Additional details on the study medication can be found in the [Investigator Brochure \(IB\)](#).

7.2. Study Medication Dosing and Administration

The CST-2032 blister cards are designed for subjects to dispense 2 tablets on each dosing day according to the treatment the subject is randomized to receive and the treatment period in which they are participating, e.g.:

- 2 placebo tablets for administration of blinded placebo, or
- 1 tablet of 3 mg CST-2032 and 1 tablet of placebo for the blinded 3 mg dose.

The CST-107 blister cards or bottles allow subjects to dispense 1 tablet on each dosing day according to the treatment the subject is randomized to receive and the treatment period in which they are participating, e.g.:

- 1 placebo tablet for administration of blinded placebo, or
- 1 tablet of 3 mg CST-107 for the blinded 3 mg dose.

During each treatment period, subjects will receive CST-107 or matching placebo for 15 days and CST-2032 or matching placebo for 14 days:

- On Day -1, CST-107 or matching placebo will be administered in clinic after completion of all scheduled assessments.
- Study drug (CST-2032 and CST-107 or matching placebos) will be administered in clinic on Day 1 during which dispensing will be demonstrated to the subjects.

Subjects will receive a 1-week supply of study drug on Days 1 and 7 of each treatment period. CST-107 or matching placebo and CST-2032 or matching placebo are to be taken together each day during both treatment periods.

